OPV III	2113512	2034476	96	2150681	2084555	92	2055735	2049333	100	2093721	2072128	99	2098904	1595884	76	1974375	1476641	75
BCG	2113512	2127471	101	2150681	2173105	94	2055735	2164062	105	2093721	2139148	102	2098904	1664981	79	1974375	1633207	83
Measles	2113512	1978350	94	2150681	1958080	90	2055735	1997355	97	2093721	1984167	95	2098904	1516299	72	1974375	1472809	75
DPT (B)	2106328	1935233	92	2148636	1972534	92	2126485	1947308	92	1703089	1869012	110	2014740	1447327	72	2253480	1462570	65
OPV(B)	2106328	1949264	93	2106328	1974875	92	2126485	1953872	92	1703089	1874653	110	2014740	1442111	72	2253480	1408211	62
DT	2180871	1957099	90	2219884	1900518	86	2329009	2064416	89	2301437	2150579	93	2458596	1724040	70	2467968	1539717	62
TT (10)	2330045	2034823	87	2371691	2067594	87	2329009	2066254	89	2492831	2226557	89	2237233	1776657	72	2467968	1492166	60
TT(16)	2150421	1875999	87	2189255	1822229	83	2126485	1922415	90	2311947	2085794	90	2244801	1585178	71	2253361	1301775	58
TT (M)	2402459	2261068	94	2444708	2143589	87	2355495	2092637	89	2398739	2061763	86	2405384	1723124	72	2254436	1246894	55

Table 2: Measles immunization coverage 2002-2007, Maharashtra State

Source: http://www.maha-arogya.gov.in/programs/nhp/mchimmunisation/performance.htm

Table 3: Immunization coverage Pune district (1996-2004)												
YEAR	BCG	DPT III	POLIO	MEASLES								
1996-1997	105	98	97	93								
1997-1998	103	98	99	100								
1998-1999	104	102	101	99								
1999-2000	110	103	103	96								
2000-2001	100	102	102	96								
2001-2002	104	100	100	99								
2002-2003	83	79	79	77								
2003-2004	55	51	51	54								

Immunization coverage for Pune district as described in Table 3 (below).

Source: http://www.maha-arogya.gov.in/projectandschemes/basic/achievements.htm

Measles is endemic in this State. There is no current active surveillance of measles cases. Reported figures include mainly data from Government hospitals. The state government is currently undertaking a project on integrated communicable disease surveillance.

Table 4, summarizes the number of cases of vaccine preventable diseases reported during the period 2002-2008.

	Surveillance of Vaccine Preventable Diseases													
Years	Diph	theria	Per	tussis	N.I	N.N.T. TB (TB (Child)		asles	Po	olio	TETANUS (O)	
	Cases	Deaths	Cases	Deaths	Cases	Deaths	Cases	Deaths	Cases	Deaths	Cases	Deaths	Cases	Deaths
2002- 03	27	2	8	0	8	2	803	22	1704	3	4	0	70	13
2003- 04	27	4	1	0	9	4	536	3	2136	30	3	0	69	14
2004- 05	206	11	58	0	14	2	468	1	1790	7	0	0	68	13
2005- 06	151	19	6	0	10	3	1062	26	1702	5	5	0	45	5
2006- 07	513	1	95	0	67	0	596	6	513	3	1	0	17	4
2007- 08 (Up to Jan.08)	497	0	37	0	10	1	142	3	341	6	2	0	26	0

Table 4: Reported cases of vaccine	preventable diseases 2	2002-2008, Maharashtra State.
------------------------------------	------------------------	-------------------------------

Source: http://www.maha-arogya.gov.in/programs/nhp/mchimmunisation/achievements.htm

Approximately 500 cases are reported from Pune city each year but this is probably a gross underestimation.

4.3.5.4 Trial setting: Vadu Rural area

The proposed study site consists of five contiguous health districts (Vadu, Wagholi, Shel Pimpalgaon, Chakan, and Kendur,) comprising over 150 villages, with a total population estimated at about 312,000 in 2007 (Table 5). The site is 30-40km across and the main village in each area is within one hour's drive from central Pune. The health districts lie within three administrative blocks (Shirur, Haveli and Khed) with Vadu spanning two administrative blocks, due to the public/private health care partnership, which is described below, paragraph 4.3.5.4. The population, location and numbers of measles vaccinations delivered in each area are shown in Table 5.

Note: Three additional health districts have been added to enhance enrolment: Nhavara, Talegaon Dhamdhere and Alandi . Information on these areas is available on request.

Table 5: Population in study area and number of measles vaccinations performed 2006-7

	Vadu	Wagholi	Shel Pimpalgaon	Chakan	Kendur	Total
Population	74000	49910	63000	99000	26865	312775
Administrative block	Shirur, Haveli	Haveli	Khed	Khed	Shirur	
Distance from Vadu Center (km)	0	15	15	25	10	
Number of EPI clinics	28	12	25	45	14	124
Number of measles vaccine doses given in 2006/07	1322	914	1000	1517	600	5353
Mean number of measles vaccine doses /month	110	76	83	126	50	446
Number of measles vaccine doses in 6 months	661	457	500	759	300	2677

Legend: EPI - WHO Expanded Programme on Immunization

4.3.5.5 Health care facilities in the Study area

Each health district area is covered by a primary health centre (PHC), which usually lies within an administrative block. Each PHC is staffed by a medical officer, nurse, and auxiliary nurse midwife (ANM).

Health care in the Vadu area is provided by the Vadu Rural Health Program, which is under the administration of King Edward Memorial Hospital and Research Centre (KEM), Pune, a privately funded hospital. One of the areas is a Demographic Surveillance Site (DSS) of the INDEPTH Network (an International Network of field sites with continuous Demographic Evaluation of Populations and Their Health in developing countries).

The District Health System is directly responsible for primary health care in the four districts. The PHCs at Kendur, Wagholi, Shel Pimpalgaon, and Chakan provide primary health care services including immunizations in their respective areas served by them. The Chakan and Wagholi PHC area are situated on major highways and are better connected similar to the Vadu area and have multiple private practitioners and small nursing homes capable of providing basic medical care. Chakan also has a rural hospital. The Kendur and Shel

Pimpalgaon PHC areas are remote and have fewer private practitioners and small private nursing homes.

The hospital in Vadu village , Shirdi Saibaba Rural Hospital (SSH), also known as Vadu Rural Hospital, is managed by the KEM Hospital and provides secondary level care to the 22 villages of the Vadu Rural Health Program. The hospital is staffed by a General Medical Officer, Obstetrics and Gynaecology specialist and resident in Obstetrics and Gynecology (all available 24hrs/day, 7days/week) with a surgeon and anesthetist available on call. A pediatrician is also employed. There are also nine registered nurses, a radiology technician and a pharmacist. A sonographer and ophthalmologist visit twice a week. On site facilities include: 7 consulting rooms; 1 male and 1 female ward; 4 patient rooms (private); 2 operating theatres; 1 labor room; 1 vaccine storage room; 1 laboratory (1 room for laboratory work, one for freezer storage); 1 X-ray room and darkroom; 1 sonography room. In addition, there is a separate research wing with a conference room, meeting hall, archive room, computer room, "outreach" room, a study room (used by the Meningococcal Vaccination Project), and a residential area.

4.3.5.6 Current measles immunization practice in the study area

Measles vaccination recommendations follow the WHO India schedule, i.e. from 9 to 12 months of age³¹.

4.3.5.7 Identification of children eligible for routine immunization

For routine immunization, health workers compile a list of eligible children every year (in March and April) based on couples eligible for contraceptive and maternal child health services where the woman is aged 15 to 49 years (eligible couples survey, register number R14). Women who become pregnant during the year are listed in the R15 register which details the services received by them during pregnancy and delivery. After delivery, the children are carried forward into the R16 register which details the vaccinations and other services like Vitamin A supplementation received by them till one year of age. A health worker allotted to each geographical area (approximately 8000 people per health worker) is responsible for following up all the eligible couples and children eligible for vaccination in that area on a monthly basis.

4.3.5.8 Procedures during routine immunization clinics

Immunization clinics are held in each village on a permanently set date for every month and clinics are held on that date even if these are holidays and Sundays. For larger villages, clinics are held on the weekly market day to ensure high coverage. The dates of immunization clinics are well known in the local population and reinforced by the local health worker.

All PHCs and SSH are equipped with an ice-lined refrigerator and a vaccine refrigerator for storage of vaccines. Vaccines are supplied by the District Health Office every month. On the immunization clinic day, vaccines are carried by the health worker to the clinic in the village from SSH or the PHC in the morning in a vaccine carrier box. At the end of the clinic, unused vaccine is returned to SSH or PHC where vaccine accountability records are maintained.

At the immunization clinic, the nurse records the child's attendance and vaccines administered in a register. After the clinic these details are transferred to the R16 register, which records the dates of all primary immunizations received by a child. The health workers perform home visits every month in the area assigned to them. A list of children who have

missed a dose is taken from the R16 register and those children are followed up during their routine monthly home visit. Data about the numbers of measles vaccinations delivered each month in the Vadu area are shown in Table 6

Table 6: Numbers of recorded births and measles vaccinations given in immunization clinic	es in
Vadu area, by month	

	Jan	Feb	Mar	Apr	May	Jun	Jul	Aug	Sep	Oct	Nov	Dec	All
Measles	96	94	111	98	122	104	105	113	98	87	111	106	1245
(range)	(0-	(0-	(1 - 18)	(0-	(0-	(0-	(0-22)	(0-22)	(0-18)	(0-	(0-	(0-	(10-
	19)	18)	18)	16)	19)	19)	22)	23)	18)	15)	19)	20)	198)
Births	114	94	116	105	97	115	113	95	94	104	100	117	1264
(range)	(0-	(0-	(1-	(0-	(0-	(0-	(0-	(0-	(1-	(0-	(0-	(2-	(16-
	29)	20)	24)	22)	22)	21)	22)	19)	20)	21)	22)	21)	255)

Legend: Based on data from 20 clinics in Vadu area, collected 2006-7. No data available from two clinics.

4.3.5.9 Research experience of the KEM Hospital and Research Center

The KEM Hospital and Research Center has had a legacy of epidemiological, bio-medical and social science research lasting 20 years. Apart from large community based cohort studies on low birth weight and child survival and fetal origins of adult onset disease, SSH has undertaken community based randomized controlled trials in iron supplementation amongst children. Currently ongoing is a large randomized observer blinded vaccine trial which is assessing the safety and long term immunogenicity of a conjugate meningococcal vaccine against a licensed polysaccharide vaccine.

Vadu has extensive demographic data available from 2003, fieldworkers with experience of collecting health-related data at household level, and experience of designing and conducting large epidemiological studies. The most recent complete census was conducted in July 2007, and updates are conducted every six months. There is currently Geographical Information System (GIS) data available for Vadu (the central village).

5 Trial objectives and purpose

The overall aim of the study is to demonstrate that measles vaccine delivered as an aerosol to the respiratory tract is sufficiently safe and immunogenic to obtain licensure for the nebulizer/vaccine combination device.

5.1 Study Rationale

A large, well-designed and -conducted, randomized controlled trial of the immunogenicity and safety of aerosolized measles vaccine in infants receiving a first dose of measles vaccine is required, in a setting where the vaccine would be used in practice.

An active control vaccine is required because the current subcutaneous vaccine is known to be highly effective and safe and is recommended worldwide. The immunogenicity of aerosolized measles vaccine should be shown to be non-inferior to the subcutaneous vaccine, according to

a pre-determined maximum acceptable difference. Superiority is not a realistic endpoint due to the high levels of serological response produced by subcutaneous vaccine.

5.2 What this trial will add

This trial has been designed to fulfil the regulatory requirements for licensing of a nebulizer/vaccine combination device, if the immunogenicity of aerosolized measles vaccination is shown to be non-inferior to subcutaneous vaccine in the target age group, and has an acceptable safety profile. By conducting the trial in a setting where the new delivery device would be used, existing public health surveillance systems will be strengthened, capacity will be built in the trial area for conducting large scale clinical trials and for the handling and serological processing of large numbers of blood samples.

5.3 Primary objectives

5.3.1 Immunogenicity

To compare the immunogenicity of measles vaccine delivered via a nebulizer/vaccine combination product with a licensed subcutaneous vaccine in infants who are eligible to receive a first dose of measles vaccination but are no older than 12 months.

5.3.2 Safety

To describe the frequency of adverse events following measles aerosol and subcutaneous vaccination.

5.4 Secondary objectives

5.4.1 Immunogenicity

To compare geometric mean antibody titres in infants receiving measles vaccine delivered via a nebulizer/vaccine combination device with subcutaneous measles vaccine;

To compare the immunogenicity of measles vaccine delivered via a nebulizer/vaccine combination device with subcutaneous measles vaccine, according to level of pre-vaccination antibody titre;

To collect blood from subset of children at 28 days and one year after vaccination. These subset will be randomly selected from all children enrolled in the Vadu study area because they will be able to be followed up within the infrastructure of an existing demographic and health surveillance system. For these subsets, the secondary objectives are:

- To compare the immunogenicity of measles vaccine delivered via a nebulizer/vaccine combination device with subcutaneous measles vaccine one year after vaccination;
- To describe the evolution of the antibody response to measles vaccine delivered via a nebulizer/vaccine combination device and subcutaneously over time, at days 0, 28, 91, 364 after vaccination;

5.4.2 Safety

To describe the frequencies of individual adverse events following measles aerosol and subcutaneous vaccination.

6 Trial design

6.1 Type/design of study

Randomized, open-label, active-control, parallel group, non-inferiority trial (Figure 1).

Figure 1: Study Flow Chart from Day 0 to Day 364

6.2 Primary and secondary endpoints

6.2.1 Immunogenicity

6.2.1.1 Primary outcome

Measles seropositivity at day 91 post-vaccination.

6.2.1.2 Secondary outcomes

For all infants:

- Geometric mean titres, pre-vaccination and at day 91;
- Seroconversion (defined as a change from Enzygost OD <0.1 to OD ≥0.1 or PRNT from <120 to ≥120 mIU/mL) measured in paired samples from day 0 and day 91;

For infants from Vadu in 28 and 364 days subset:

- Geometric mean titres at days 28 and 364 to describe evolution of antibody response at days 0, 28, 91, 364;
- Seropositivity at 364 days in infants with antibody titre \geq 120 mIU/ml at day 91.

6.2.2 Safety

6.2.2.1 Primary outcome

Adverse events up to and including day 91 post-vaccination;

Adverse events include acute clinical reactogenicity, other adverse events, and serious or unexpected adverse events.

6.2.2.2 Secondary outcome

Frequencies of individual adverse events

6.3 Measures taken to minimize bias

6.3.1 Randomization

See SOP VEL 4/1

6.3.1.1 Unit of randomization

Individual child

6.3.1.2 Sequence generation

The allocation sequence will be computer-generated random numbers, in permuted blocks, generated by an independent statistician. The randomization ratio will be 1:1.

6.3.1.3 Allocation concealment

Allocation will be accessed by telephone from the study enrolment site to an operator with a secure web-based system. Allocation will be recorded in the system, along with the unique patient data.

6.3.1.4 Implementation

- A doctor or study nurse at each health centre will obtain the allocation and record it immediately in the Day 0 case report form (CRF).
- The intervention is administered accordingly.

See SOP VEL 2/1 for details of quality assurance, and ensuring that correct allocations have been administered.

6.3.2 Blinding

The trial is open-label and the routes of administration different, so blinding of participants and investigators will not be possible.

6.3.2.1 Blinding of safety assessment

It will not be possible to guarantee the blinding of assessors of safety outcomes. Parents/guardians of participants will know which vaccination route their child received. To minimize bias there will be no record of intervention allocation on CRFs for follow up visits and parents/guardians will be asked identical structured, non-leading questions.

An independent Data Safety and Monitoring Board (DSMB) will have access to unblinded data for the assessment of serious adverse events.

6.3.2.2 Blinding of immunogenicity assessment

Laboratory staff will be blinded to allocation to aerosol or subcutaneous administration (see SOP VEL 3/1 for details).

6.3.2.3 Blinding during laboratory testing

- Blood samples will be labelled with a barcode unique to the patient and blood drawing date, but the patient and sample number (e.g. second sample from this individual) will not be identifiable without the data-linking documents.
- The barcode numbers will be generated at CMC Vellore and the data-linking documents held there. Blood samples and additional identical barcodes will be transported together to the site of serum aliquotting (post serum-separation).
- Each aliquot will be labelled with the same barcode as the original sample. As blood samples will be drawn from both subcutaneous and aerosol vaccine recipients on blood collection days, there will be no predictable pattern (relating to intervention group) in sample receipt at the laboratories for ELISA and PRN testing.
- Test runs will include specimens from both subcutaneous and aerosol arms. As the lab/s conducting the ELISA and PRN tests will have not participated in blood collection and labelling and will have no access to linking data, they will remain blinded.

6.4 Description of the trial combination product (vaccine-aerosol delivery device) and dose

All children will receive monovalent Edmonston-Zagreb (E-Z) strain attenuated measles vaccine manufactured by the Serum Institute of India, Ltd (SIIL).

6.4.1 Dosage form, packaging and labelling of the vaccine

6.4.1.1 Live attenuated measles vaccine

The dose of measles live attenuated lyophilized E-Z vaccine will be not less than 1000 CCID₅₀ per dose). The vaccine also contains excipients/stabilisers.

6.4.1.2 Diluent

The diluent for the vaccine is water for injection (WFI). Bulk WFI is prepared by distillation and meets the Indian Pharmacopoeia specifications for WFI.

6.4.1.3 Method of packaging and labelling of the vaccine

Vaccine vials for the aerosol arm will be labelled and packaged to indicate that they are for the clinical trial.

A sample of the label for the aerosol vaccine is shown below:

6.4.2 Vaccine lots

Vaccine lots will be selected as follows:

Item	Batch	Doses	Presentation	Label
Aerosol Vaccine	1	500	50 x 10 dose vials	Clinical label - research only
Aerosol Vaccine	erosol Vaccine 2		50 x 10 dose vials	
Aerosol Vaccine	3	500	50 x 10 dose vials	
Aerosol Vaccine	4	1000	100 x 10 dose vials	
Aerosol Diluent	А	1500	150 x 2.5 mL amps	Clinical label stating for aerosol vaccine reconstitution only
Subcutaneous Vaccine	1	1500	150 x 10 dose vials	Regular label
Aerosol Diluent	В	2500	250 x 2.5 mL amps	Clinical label stating for aerosol vaccine reconstitution only
Subcutaneous Diluent	В	1500	150 x 5 mL amps	Regular label

All lots will have an expiry date of at least 18 months from date of shipping to the research center. Ten vials of each vaccine batch and 30 ampoules of each diluent batch will be retained by the vaccine manufacturer for retesting.

6.4.2.1 Vaccine delivery device

Aerosolised vaccine will be delivered using the Nektar device (Aerogen/Nektar, San Francisco, See Appendix 1 for full details) to be included.

6.4.2.2 Method of packaging and labelling of the device

A sample of the device over-label is shown below:

6.5 Expected duration of subject participation and description of sequence and duration of trial periods including follow-up.

Duration of subject participation

- Every child will be followed for 91 days after vaccination for ascertainment of the primary immunogenicity and safety outcomes.
- Additionally, all children in the Vadu area will be followed to 364 days after vaccination for ascertainment of adverse events.
- A random subset of 100 of children in each arm from the Vadu area will have blood drawn at day 28 and day 364.
- A random subset of 100 of children in each arm from the Vadu area will have blood drawn at day 364. The selection of this group will be independent from the selection for the day 28 blood sample and individuals my be selected for blood sampling on both day 28 and 364.

Enrolment period

It is estimated that it will take approximately six months to enrol 2000 participants, based on a 50-80% participation rate. This is assumes that approximately 100 infants will be screened for inclusion in the trial per week.

Duration of follow up periods

The expected duration of the study from initial enrolment to the primary outcome (day 91 visit) is nine to 12 months, based on the enrolment rate above and, the assumption that the number of children available for vaccination is similar to that in previous years.

Duration of the study from initial enrolment to the secondary outcome (day 364 visit) for the subset of children in the Vadu area is 18 to 21 months.

Detailed information on the planned follow-up visits is in Section 8.4.4 including Table 7.

6.6 Stopping rules or discontinuation criteria

The trial will be discontinued according to the stopping rules determined by the DSMB (Appendix 2: Terms of Reference of the Data and Safety Monitoring Board). The criterion for discontinuation is the occurrence of a single SAE or encephalitis/encephalopathy in one or more subjects which is deemed to be most probably related to the aerosol vaccine.

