4.3.2 Summary of known and potential risks and benefits to human subjects

The expected risks include those already known to be associated with parenteral measles vaccination. For instance, a mild measles-like illness may follow vaccination. The most common side effects include fever and rash; these occur in 5-15% and 5%, respectively, of persons vaccinated subcutaneously.¹¹⁻¹⁴ Cough and conjunctivitis may also occur. Thrombocytopenia (platelet count <50,000/mL) occurs in less than one in 30,000 vaccinees approximately 2 weeks post-vaccination and may be more common in persons with a history of immune thrombocytopenia purpura. Only rarely, has this complication been associated with bleeding.¹⁵⁻¹⁹ There is also a risk of encephalitis/ encephalopathy in one of 87,000 to 2,000,000 doses. There has been some controversy regarding whether or not the relationship is causal or coincidental. Nonetheless, cases have clustered in the first 1-2 weeks post-vaccination and may occur up to a month later. In addition, some persons have experienced long-term neurological sequelae.²⁰⁻²⁴ As this is a live-attenuated virus vaccine, persons with deficient cell-mediated immunity should not be vaccinated and women who are pregnant should not receive this vaccine secondary to the theoretical risk of fetal infection.

Over the last several years, there has been concern over the possible association between measles vaccination and autism and inflammatory bowel disease. However, carefully conducted studies have failed to confirm these findings and there is no evidence that measles vaccine is associated with or causes these diseases.²⁵⁻²⁸

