4.3.2.1 Potential Central Nervous System Effects

Rarely, natural measles infection may be associated with CNS disease, namely encephalitis and sub-acute sclerosing pan encephalitis (SSPE). In contrast, attenuated measles vaccine is not associated with SSPE; on the contrary, measles vaccine is protective against SSPE. There is concern as to whether attenuated vaccine might reach the brain of aerosol vaccinees by retrograde transport via the olfactory nerve fibers. There is also the theoretical risk of exposure of the nasal mucosa to replicating vaccine virus and the possibility of central nervous system side effects due to passage through the cribiform plate of the ethmoid bone. This is an unlikely probability given the extensive public health experience with its use in Mexico. As many as 4 million children have been vaccinated by this method and no serious adverse events, including encephalitis, encephalopathy and death, have been reported. Heretofore, there have not been reports of CNS problems in the large aerosol measles vaccine experience. In addition, during the animal studies described above, no abnormalities in gross pathology or histopathology related to measles infection were detected in any of the organ studied. Furthermore, none of the organ samples tested by a semi quantitative RT-PCR showed measles virus genome including samples of the cribiform plate and an additional sample of the nervus olfactorious with a small piece of the olfactory bulb.

Therefore, there is no available evidence to indicate that the frequency of central nervous system side effects will be greater than that seen among measles non-immune persons receiving measles vaccine parenterally. However, the surveillance of adverse effects includes the search for neurological effects including data indicative of encephalitis or encephalopathy.

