8.7.6 Classification of association of events with vaccination

The investigator will assess whether any adverse event is related to the immunization using the following scale and according to the following definitions (based on Workbook for Investigators, WHO/TDR).

- Not related: The event is clearly related to other factors such as the patient's clinical state, therapeutic intervention or concomitant therapy.
- Unlikely to be related: The event was most probably produced by other factors such as the patient's clinical state, therapeutic intervention or concomitant therapy, and does not follow a known response pattern to the study vaccine.
- **Possibly related:** The event follows a reasonable temporal sequence from the time of study vaccine administration and/or follows a known pattern to the study vaccine but could have been produced by other factors such as the patient's clinical state, therapeutic intervention or concomitant therapy.
- **Probably related:** The event follows a reasonable temporal sequence from the time of study vaccine administration and/or follows a known response pattern to the study vaccine and could not have been produced by other factors such as the patient's clinical state, therapeutic intervention or concomitant therapy. These events include but are not limited to those that require medical attention and result in withdrawal from follow-up. Any available medical records needed to accurately describe the event will be obtained from the appropriate health care provider.
- **Most probably related:** The event follows a reasonable temporal sequence from the time of vaccine administration; and/or follows a known response pattern to the trial vaccine; and could not have been produced by other factors such as the patient's clinical state, therapeutic intervention or concomitant therapy; and either occurs immediately following trial vaccine administration, or there is positive reaction at the application site.
- **Insufficient data to assess:** There is not enough clinical and/or laboratory information to suggest the relationship between the experience and the trial product.

A report on all **Severe** Adverse Events and all **Serious** adverse events will be submitted to the DSMB within 7 days, following the Terms of Reference of the DSMB for the Measles Aerosol Project (Appendix 2). The DSMB will make the final decision on the classification of serious and severe adverse events.

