Vomit																	1												1									1	\square		i T						
Wheeze																1	1		1														1					\mathbf{T}	\square		i						

SOP VEL 1/1:	Statistical Analysis Plan	Page 47 of 61
Sep 2012		

15.0 Trial Termination:

The trial will be terminated according to the stopping rules determined by the DSMB. The criterion for termination is the occurrence of the single serious adverse event or encephalitis/encephalopathy in one or more subjects which is deemed to be most probably related to the Aerosol vaccine.

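### The stopping criterion in protocol 6.6 and SAP 15.0 normally cannot fire for encephalitis at its expected onset, and protocol 11.3 prints a conflicting rule

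*Supplement*

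**What the plan says.** Protocol 6.6 makes the criterion for discontinuation the "occurrence of a single SAE or encephalitis/encephalopathy in one or more subjects which is deemed to be most probably related to the aerosol vaccine". SAP 15.0 uses the same grade, ending in "encephalitis/encephalopathy in one or more subjects which is deemed to be most probably related to the Aerosol vaccine". Both sections refer to stopping rules determined by the DSMB. Protocol 6.6 and 11.3 place those rules in Appendix 2, which the appendix list says was updated on 26 November 2009 to a DSMB charter. Its text is not shown.

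The grades come from protocol 8.7.6. For *probably related*, the event fits the time sequence and/or "follows a known response pattern to the study vaccine and could not have been produced by other factors". For *most probably related*, those elements are repeated and one more is added: "and either occurs immediately following trial vaccine administration, or there is positive reaction at the application site". The same section says "The DSMB will make the final decision on the classification of serious and severe adverse events".

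On encephalitis, protocol 4.3.2 gives a "risk of encephalitis/ encephalopathy in one of 87,000 to 2,000,000 doses" and says "cases have clustered in the first 1-2 weeks post-vaccination and may occur up to a month later". Section 4.3.2.1 adds that "the surveillance of adverse effects includes the search for neurological effects including data indicative of encephalitis or encephalopathy".

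Protocol 11.3 states the rule differently. It ends the trial on one reported SAE that is attributable to the aerosol vaccine. *Attributable* is not one of the six grades in 8.7.6, and 11.3 does not mention encephalitis.

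**The concern.** Encephalitis/encephalopathy is the only event that 6.6 and SAP 15.0 name. Section 4.3.2.1 explains why: there is a theoretical route to the brain through the nasal mucosa and olfactory nerve. Follow-up is built to find delayed onset, with home visits on days 3, 7 and 10 and a clinic visit with a directed neurological examination on day 14/15. Yet the grade that triggers the stop depends on immediate onset or a reaction at the site, neither of which is how the protocol expects this event to present.

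At stake is whether the DSMB, the investigator and the sponsor would read the same answer from the plan on the day a case occurs. As printed, two passages say the criterion is not met and a third says that it is. A single-event stopping rule should not need interpretation at that moment.

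**Working it through.** The stopping rule states no figure, so the main check compares wording. Take one illustrative case: an aerosol infant is hospitalised with encephalitis starting on day 10, no other cause is found, and there is no application-site reaction.

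**Grade under 8.7.6 as written**
- Time sequence or known pattern: met. Day 10 lies in the window given in 4.3.2.
- Could not have been produced by other factors: met by construction. *Probably related* is reached.
- Immediate onset: not met. The protocol's only definition using that word (immediate adverse events, 8.7.1) is 30 minutes, and day 10 is not immediate on any ordinary reading.
- Application-site reaction: absent by construction. The text shown does not define it for an inhaled product.

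The case stops at *probably related*.

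**What each printed rule does with it**

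| Place | Requirement | Result |
|---|---|---|
| Protocol 6.6 | *most probably related* | not met |
| SAP 15.0 | *most probably related* | not met |
| Protocol 11.3 | SAE *attributable* to the aerosol vaccine | met on a plain reading: hospitalisation makes it an SAE, and other causes are excluded |

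The grammar of 6.6 allows the grade to attach to both events or to encephalitis/encephalopathy alone. Encephalitis carries the grade either way, so the result is the same.

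**How often this could arise**

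Inputs: 1 in 87,000 to 1 in 2,000,000 doses (4.3.2, parenteral vaccine; assumed to hold for aerosol) and 1000 aerosol infants (2000 enrolled, 1:1).

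P(at least one case) = 1 − (1 − rate)^1000
- Highest rate: 1 − (1 − 1/87,000)^1000 = 0.0114, or 1.1%.
- Lowest rate: 1 − (1 − 1/2,000,000)^1000 = 0.0005, or 0.05%.

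**What one case would mean**

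The plan's own limit for no events in 1000 reproduces: 1 − 0.025^(1/1000) = 0.00368, against 0.37% in 11.2.2. For one event in 1000, the exact 95% interval is:
- lower limit 1 − 0.975^(1/1000) = 2.53 × 10⁻⁵, or 1 in 39,500;
- upper limit 0.00556, or 1 in 180.

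The lower limit divided by the highest quoted rate is 2.53 × 10⁻⁵ × 87,000 = 2.2. One related case would already lie above the quoted range, so a single-case trigger for this event is sensible.

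**The case against.** The strongest reply is that the governing rule is not in front of us. Sections 6.6, 11.3 and SAP 15.0 all defer to the DSMB's rules, and the charter may be wider than any of them. That stands as a limit on the point. It does not remove it: the SAP is dated September 2012, almost three years after the charter update, and still prints *most probably related*. If the charter is wider, 6.6 and SAP 15.0 misstate it.

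Second, 11.3 already covers the case. This also stands, and it rules out a stronger reading. A reader might infer that aerosol vaccination would simply continue after a delayed encephalitis case. The documents do not support that. Section 11.3 read plainly calls for a stop, SAEs are to reach the DSMB quickly (8.7.2, 8.7.3), and the DSMB makes the final classification. What 11.3 does not do is settle the matter, because it is tied to no grade and contradicts 6.6.

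Third, *application site* is undefined for an inhaled product. If conjunctival reactions counted, more cases could reach the top grade: 4.3.2 reports them in 34 of 59 aerosol infants in an earlier study. That is possible, but it would make the stop for encephalitis depend on an unrelated eye reaction.

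Fourth, the threshold is a judgement. Section 4.3.2 says causality has been debated, so a single case might be graded only *possibly related*, and the change proposed here would not stop the trial for that. This is fair. The proposal removes the mismatch between grade and onset. It does not claim that its threshold is the only defensible one.

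**Conclusion.** The printed plan contains two conflicting stopping rules, and one of them normally misses the event it names. On the 8.7.6 scale as written, encephalitis/encephalopathy with typical onset and no site reaction cannot meet 6.6 or SAP 15.0, yet it meets a plain reading of 11.3.

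The probability is small: 0.05% to 1.1% for any case in 1000 aerosol infants. This assumes that the parenteral rates carry over to the aerosol route, which the trial itself has to examine. The conclusion also assumes that the DSMB applies 8.7.6 as written and that the unseen charter does not set a different rule. It should be corrected because the event is the one singled out for stopping and the correction is nearly free. It has no bearing on the immunogenicity analysis.

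**What to change.** Put one criterion in protocol 6.6, protocol 11.3 and SAP 15.0, after checking it against the DSMB charter:

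> The trial will be discontinued if the DSMB classifies one SAE as most probably related to the aerosol vaccine, or one case of encephalitis/encephalopathy as probably or most probably related to it. No immediacy or application-site condition applies to encephalitis/encephalopathy.

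In 11.3 this replaces *attributable*. For other SAEs it keeps the threshold of 6.6 and SAP 15.0. If the charter shows that the broader sense of 11.3 was intended for all SAEs, that sense should be written into all three places instead. Grouping the top two grades is already familiar to the DSMB, since SAP Tables 14.0.2 and 14.0.3 report them together.

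The cost is wording plus a routine protocol amendment, which under 14.1 needs prior written ethics approval. No new data or coding are needed. The statistical price is a slightly more sensitive stop for one event. At the quoted rates, and if those rates cover every case the DSMB would grade *probably related* or higher, it adds at most about a 1.1% chance of stopping.
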